5.2.5 Smoking as Usual Period for Smoking Group (~days 1-3 or 29-31)

Participants will be instructed to smoke as usual during this period. They will make the same visits to the Center and complete the same measures during the mandatory abstinence period. As in our prior studies, to minimize deprivation and standardize exposure on the scanning day (day 4 or 32), participants will be instructed to smoke immediately prior to entering the scanner building (accompanied by a research technician). There will be ~45 minutes between this cigarette smoked and the beginning of the imaging session in the smoking as usual period.

5.2.6 24-Hour Dietary Recalls:

On days 2-4 and 30-32, a trained member of the research staff will use a multi-pass method with an interactive computerized software program, the ASA24® (Automated Self-Administered 24-hour Recall), to determine total kcal/day. If participants are unable to complete a scheduled recall over the telephone or are onsite for a scheduled visit, participants may be asked to complete a 24-hour dietary recall with the research staff in-Center.

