2.2 Overall Objectives - (Recruitment & Retention Pilot Study)

Aim 1: To evaluate the effects of information provision and incentives, alone and in combination, on study enrollment rates.

Hypothesis: Behavioral economic interventions will (Information provision & contingency management) will produce higher rates of enrollment compared to standard recruitment.

3 Study Design

General Design – Main Study

This is a within-subject cross-over neuroimaging investigation of 3 potential neural mechanisms of increased caloric intake during initial smoking cessation. Eighty smokers will be scanned on 2 occasions: (1) after 4 days of monitored abstinence (biochemically verified), and (2) after 4 days of smoking as usual (order counterbalanced) (**Figure 3**). In addition, 30 healthy non-smokers (matched for sex, age, and education) will complete one period of the study to serve as a baseline comparison group (see Exploratory Aim). As in prior studies, participants will have fasted overnight and be provided with a standard meal (BOOST® shake) when they arrive on testing days 4 and 32. Blood oxygen level dependent (BOLD) fMRI sessions will assess BOLD signal at rest and while performing tasks for food cue reactivity, food reinforcement (choice task), and working memory (N-back). Additional measures will be administered out of scanner (**Figure 3**). Caloric intake will be assessed on days 1-3 and 29-31 using a validated dietary recall procedure (days 4 and 32 are fMRI scan days and intake will be standardized). Caloric intake is the primary behavioral outcome. Task-induced BOLD signal change in hypothesized regions of interest and performance on the working memory, food cue, and food reinforcement tasks are the mechanistic variables.

CONFIDENTIAL

This material is the property of the University of Pennsylvania. Do not disclose or use except as authorized in writing by the study sponsor

Figure 3

Non-smoker Control Group (Baseline):

Day	-7	1 2 3 4
Activity	Intake	Period 1*

*non-smokers complete phase 1 with identical monitoring and assessment

**order of periods (abstinence vs smoking) is counter balanced

Smoker Group (within-subject):

Day	-7	1 2 3 4	5-28	29 30 31 32	1 Month Follow-up
Activity	Intake	Period 1	Washout	Period 2	Web-based Survey
State	Smoke	Abstain**	Smoke	Smoke	N/A

Behavioral Outcome:

- Caloric intake (dietary recall; Days 1-3* & Days 29-32)

Intermediate Outcomes: Day 4* & Day 32

- Food reward (out of scanner)
- Working memory (fMRI)

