4.3 Inclusion Criteria

1. Male and female participants who are between 18 and 65 years of age.
 1. Smoking group – 80 smokers who self-report smoking at least 5 cigarettes (menthol and/or non-menthol) per day for at least the last 6 months. Smoking status will be confirmed by CO greater than or equal to 8 parts per million (ppm) at the Intake Visit.
 2. Non-smoking group - 30 individuals reporting fewer than 100 lifetime cigarettes and not even a puff of a cigarette for a minimum of 2 years. Smoking status of non-smokers will be confirmed by CO less than 5ppm. They will be matched to the smoker group on age, sex, and education.
2. Plan to live in the area for the duration of the study (i.e. ~8 weeks/2 months).
3. Capable of giving written informed consent, which includes compliance with the requirements and restrictions listed in the combined consent and HIPAA form.
4. Able to communicate fluently in English (i.e. speaking, writing, and reading).

CONFIDENTIAL

This material is the property of the University of Pennsylvania. Do not disclose or use except as authorized in writing by the study sponsor

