5.2.4 Mandatory Abstinence Period for Smoking Group (~days 1-3 or 29-31)

Participants will be randomized with respect to the order of the study periods; one-half of participants will have their mandatory abstinence period on days 1-4 and one-half will have this period on days 29-32. On the evening prior to the mandatory abstinence period, participants will receive a 20-minute structured telephone counseling session from a trained smoking cessation counselor to prepare for the upcoming 4-day abstinence period. Quit strategies include identifying triggers and alternative behaviors to smoking, deep breathing, and stimulus control methods. The abstinence periods will be framed as "practice quit attempts" unaided by nicotine replacement therapy or other medication.

On study days 1-3 (period 1) and 29-31 (period 2), participants will come to the Center and complete measures that may include a CO reading, breath alcohol test (BrAC), and questionnaires (smoking behavior, urges, mood, withdrawal, eating). Please see measures

CONFIDENTIAL

This material is the property of the University of Pennsylvania. Do not disclose or use except as authorized in writing by the study sponsor

table for specific time points. To verify smoking abstinence participants must have a CO reading of <10ppm or >50% reduction from their intake CO value on day 1 (or 29) and a CO reading of <5ppm on days 2, 3, or 4 (or 30, 31 & 32). Participants that do not meet CO criteria, have a BrAC greater than 0.000, or a positive urine drug screen will be withdrawn from the study, unless the Principal Investigator permits the participant to reschedule the visit to a later date.

Day 1/Day 29 Back-up Scheduling: Some participants may choose to be scheduled as a back-up for another participant's Day 1 or Day 29 visit. This is done to ensure that this protocol is efficiently using the time that is reserved on the fMRI scanner days at Days 4 and 32. Participants who are scheduled as a back-up should prepare for their back-up Day1/Day 29 in the same way that they would prepare for a primary visit. On the day of the back-up, participants should arrive at the Center in the smoking state that they have been assigned to for their respective Day 1/Day 29. Upon arrival participants will go through the same visit check-in to verify eligibility for the visit.

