5.2.7 Washout Period for Smoking Group (~days 5-28)

Between study periods there is a "washout period" (days 5-28) when participants will smoke as usual. No study visits will occur during this time.

5.2.8 fMRI Scan Visits 1 & 2 (~days 4 and 32)

Prior to each scan, participants will be instructed to fast overnight (beginning at ~10pm) until after the completion of their fMRI scanning visit the following day. The fast period will include a Boost® Nutritional Drink (Vanilla) that will be provided during the scanning visit to standardize prior food intake and remove deprivation to increase sensitivity to changes in food reward. Since participants are asked to fast overnight, all scanning sessions will be scheduled to occur in the morning. However, a scan may be completed in the afternoon at the discretion of the Principal Investigator due to extenuating circumstances. Additionally, participants will be instructed not to consume caffeine for 4 hours prior to the beginning of the visit in order standardize satiety. Including the 1-hour fMRI scan, scanning visits are expected to last ~4 hours in duration. If a scanner hardware/software malfunction occurs and data is unable to be collected, an fMRI scan(s) may be rescheduled at the discretion of the Principal Investigator.

CONFIDENTIAL

This material is the property of the University of Pennsylvania. Do not disclose or use except as authorized in writing by the study sponsor

At both scanning visits participants will:

1. Complete a urine drug screen (at least 30ml [two tablespoons] of urine). The urine drug screen will assess the use of any study-prohibited medications/recreational drugs (See Key Exclusionary Criteria; Alcohol/Drugs). Participants who test positive for any study-prohibited medications/recreational drugs will be deemed ineligible for the study at the discretion of the Principal Investigator.
2. Self-administer a CLIA-waived urine pregnancy test (female participants only). Participants who believe that they may be pregnant are instructed to discontinue participation in the study at this time.
3. Perform a BrAC assessment to control for alcohol consumption.
 - Participants with a BrAC greater than 0.000 will be ineligible to complete the study unless the Principal Investigator permits the participant to reschedule the neuroimaging scan to another day.
4. Perform a CO breath assessment

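### No rule or analysis confirms that smokers who abstain first are back to usual smoking in period 2, so the mean abstinent-minus-smoking difference may shrink in that sequence by an unknown amount

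*Combined protocol and SAP*

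**What the plan says.** Section 3 (General Design – Main Study) sets up a two-period crossover: "Eighty smokers will be scanned on 2 occasions". Section 5.2.4 splits the order evenly: "one-half of participants will have their mandatory abstinence period on days 1-4 and one-half will have this period on days 29-32". The two states are then handled differently.

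- **Abstinence period (5.2.4).** "To verify smoking abstinence participants must have a CO reading of <10ppm or >50% reduction from their intake CO value on day 1" (or day 29), followed by "a CO reading of <5ppm on days 2, 3, or 4 (or 30, 31 & 32". Those who fail "will be withdrawn from the study, unless the Principal Investigator permits the participant to reschedule the visit to a later date". A counselling call comes the evening before, and the period is presented to participants as a rehearsal for quitting.
- **Smoking-as-usual period (5.2.5).** "Participants will be instructed to smoke as usual during this period". The same visits and measures apply, with one accompanied cigarette about 45 minutes before the scan. No CO value or cigarette count is required.
- **Washout (5.2.7).** Participants are to smoke as usual on days 5-28. "No study visits will occur during this time".
- **CO floor for smokers.** It applies at entry only: "Smoking status will be confirmed by CO greater than or equal to 8 parts per million (ppm) at the Intake Visit" (4.3).
- **Data collected.** Table 2 has CO and TLFB on days 1-4 and 29-32 for smokers. Section 5.3.1 gives confirmation of smoking status as the purpose of the CO readings, and Figure 3 labels smoking behaviour as CO-verified.
- **Analysis (5.6).** Aim 1 uses abstinent-minus-smoking difference scores. The optional covariates are sex, BMI, nicotine dependence, age and weight concerns. Sequence appears only under Missing Values, as a descriptive look at dropout.

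**The concern.** A within-subject difference is only as good as both of its states, and here just one is verified. The exposure is one-sided. About 40 of the 80 smokers reach their smoking period after counselling, four verified days without cigarettes and 24 days without a visit. The other 40 have had none of this when their smoking period is measured. A participant who has cut down can attend days 29-31, report a low rate, give a low CO reading and still be analysed as smoking as usual, because no value is defined as too low. The primary behavioural outcome is then compared with a reference that is partly abstinent. The plan has a washout to prevent this but no step that shows whether it worked.

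**Working it through.** **1. Why counterbalancing does not cancel it.** Let T be the true abstinent-minus-smoking difference, P the period 1 minus period 2 effect, f the share of abstain-first smokers who have not resumed, and r the share of the contrast they keep.

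- Abstain-first mean difference: T + P − f(1−r)T
- Smoke-first mean difference: T − P
- Average of the two: T × [1 − f(1−r)/2]

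The period effect cancels; the carry-over does not. The gap between sequences is 2P − f(1−r)T, so a sequence term alone cannot separate carry-over from a period effect. Smoking data are needed for that.

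**2. Reproducing the plan's power (5.5).** I used a two-sided one-sample t test on difference scores, with noncentrality d√n and n = 80.

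| Statement in 5.5 | d | alpha | Power |
|---|---|---|---|
| Cessation increases food intake | 0.32 | 0.05 | 0.807 |
| H1a and H1b | 0.36 | 0.02 | 0.799 |
| H1c | 0.37 | 0.0167 | 0.804 |

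For the intake test, noncentrality is 0.32 × √80 = 2.862 against a critical value of 1.990. With n = 110 all three powers are 0.91-0.92, so the stated 80% belongs to the 80 smokers and has almost no reserve.

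**3. Dilution of the intake test.** The documents give neither f nor r. I assume f = 10% or 20% (4 or 8 of 80) and r = 0.5 (cut down) or 0 (no contrast left). Diluted d = 0.32 × [1 − f(1−r)/2].

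| f | r | Diluted d | Power |
|---|---|---|---|
| 0 | – | 0.320 | 0.807 |
| 10% | 0.5 | 0.312 | 0.787 |
| 20% | 0.5 | 0.304 | 0.766 |
| 10% | 0 | 0.304 | 0.766 |
| 20% | 0 | 0.288 | 0.721 |

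Adding the extra variance from mixing affected and unaffected smokers lowers these by at most 0.004.

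**4. The Aim 1 test is a different test.** Section 5.6 tests the slope of caloric-intake change on BOLD change, not a mean. I simulated n = 80, alpha 0.0167, an assumed within-group correlation of 0.35, and mean shifts of 0.37 (BOLD) and 0.32 (intake). With 0, 20 and 40% of abstain-first smokers showing no shift in either measure, slope power was about 0.80, 0.82 and 0.83. There was no loss.

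**5. Would dropping the affected smokers help?** Power for the intake test:

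| f | Dropped (n) | Kept, r = 0.5 | Kept, r = 0 |
|---|---|---|---|
| 10% | 0.786 (76) | 0.787 | 0.766 |
| 20% | 0.764 (72) | 0.766 | 0.721 |

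Dropping helps only when the contrast is nearly gone. For smokers who have cut down but keep half the contrast, it gains nothing.

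**The case against.** The plan is not without safeguards. CO and TLFB are taken at these visits, so the problem would show in the data. General Exclusion item 4 in section 4.4 allows removal for significant non-compliance at any time, and washout participants are told to keep smoking. Section 4.4 also excludes people who plan to join a cessation programme or use cessation treatment, abstinence is short and unaided, and optional quit support comes only after Scan 2. These points make complete, lasting cessation less likely. They do not close the gap: each is discretionary or sets no threshold, and none shows that usual smoking had resumed on the three intake days. The check-in for back-up visits in 5.2.4 refers to the assigned smoking state but adds no smoking criterion.

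Three stronger readings are tempting, and the documents do not support them.

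- A reader might infer that someone who stayed fully quit would pass every check. The smoking scan requires a cigarette, so a complete quitter could not finish it without smoking. The pre-scan cigarette also gives the BOLD measures some recent exposure. It comes on day 32, after the intake days, and a reduced smoker can comply with it.
- A reader might infer that every within-subject objective loses power. The arithmetic applies to mean differences. The Aim 1 slope need not weaken, and Aim 2 tests incremental R².
- A reader might infer that the loss is known to be large. No resumption rate is given, and treating everyone affected as having no contrast is the worst case.

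**Conclusion.** The point holds as a gap in verification and analysis. The reference condition rests on an instruction, and smoking data collected in that period have no criterion, no consequence and no place in the models. Any carry-over lowers the mean contrast in the abstain-first sequence only, with caloric intake on days 29-31 the most exposed.

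Its size is unknown. Under the assumed 10-20% of abstain-first smokers affected, power for the intake test goes from 0.81 to 0.79-0.77 if half the contrast remains and to 0.77-0.72 if none does. These figures also assume that the smoke-first sequence is unaffected and that n = 80 is reached. The absence of slope-power loss rests on an assumed correlation of 0.35. The gap itself does not depend on these assumptions. It should be corrected, but it is not evidence that the main contrast is materially biased.

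**What to change.** - **Flag.** In 5.2.5, pre-specify a smoking-state verification flag from data already collected. One example is CO at or above the trial's own 8 ppm intake threshold on day 1 (or 29), together with a TLFB rate over the smoking period at or above a stated share of the Baseline rate. Both parts are needed: a day-1 reading of 8 or 9 ppm also meets the abstinence limit in 5.2.4.
- **Washout.** Take the day-29 TLFB back over days 5-28.
- **Analysis.** In 5.6, keep all completers as the primary set, add a sequence term to the difference-score models, report flag failures by sequence, and pre-specify a sensitivity analysis limited to verified smoking periods.

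Exclusion should not define the primary set. It selects on behaviour after randomisation, falls mainly on one sequence, and gains nothing for smokers who keep half the contrast. The flag is for analysis only; no participant is asked to change smoking.

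The cost is a protocol sentence, one data-system flag, a slightly longer TLFB at day 29 and one extra analysis. The verified set will be smaller and partly selected by sequence, so it should be read beside the primary result.

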5.2.7 Washout Period for Smoking Group (~days 5-28)

Between study periods there is a "washout period" (days 5-28) when participants will smoke as usual. No study visits will occur during this time.

5.2.8 fMRI Scan Visits 1 & 2 (~days 4 and 32)

Prior to each scan, participants will be instructed to fast overnight (beginning at ~10pm) until after the completion of their fMRI scanning visit the following day. The fast period will include a Boost® Nutritional Drink (Vanilla) that will be provided during the scanning visit to standardize prior food intake and remove deprivation to increase sensitivity to changes in food reward. Since participants are asked to fast overnight, all scanning sessions will be scheduled to occur in the morning. However, a scan may be completed in the afternoon at the discretion of the Principal Investigator due to extenuating circumstances. Additionally, participants will be instructed not to consume caffeine for 4 hours prior to the beginning of the visit in order standardize satiety. Including the 1-hour fMRI scan, scanning visits are expected to last ~4 hours in duration. If a scanner hardware/software malfunction occurs and data is unable to be collected, an fMRI scan(s) may be rescheduled at the discretion of the Principal Investigator.

CONFIDENTIAL

This material is the property of the University of Pennsylvania. Do not disclose or use except as authorized in writing by the study sponsor

At both scanning visits participants will:

1. Complete a urine drug screen (at least 30ml [two tablespoons] of urine). The urine drug screen will assess the use of any study-prohibited medications/recreational drugs (See Key Exclusionary Criteria; Alcohol/Drugs). Participants who test positive for any study-prohibited medications/recreational drugs will be deemed ineligible for the study at the discretion of the Principal Investigator.
2. Self-administer a CLIA-waived urine pregnancy test (female participants only). Participants who believe that they may be pregnant are instructed to discontinue participation in the study at this time.
3. Perform a BrAC assessment to control for alcohol consumption.
 - Participants with a BrAC greater than 0.000 will be ineligible to complete the study unless the Principal Investigator permits the participant to reschedule the neuroimaging scan to another day.
4. Perform a CO breath assessment
5. Self-report smoking behavior over the past 24 hours to control for prior tobacco exposure and provide their daily smoking rate (timeline follow back [TLFB]) (smokers only).
6. Have weight measured.
7. Complete a magnet safety form***.
8. Complete paper and pencil questionnaires (craving, withdrawal, mood, eating)***.
9. Complete a set of abbreviated practice tasks similar to those that will be administered during the fMRI scan. Participants will be expected to demonstrate an understanding of the tasks and the response device prior to the fMRI scan.
10. Be provided with a Boost® Nutritional Drink and water.
11. Be escorted to the imaging facility at either the Hospital of the University of Pennsylvania or the Stellar Chance building for the brain-scanning portion of the session.
12. **SMOKING SCAN ONLY:** Participants will smoke one of their own cigarettes (~45 min. before initiating fMRI) in a designated smoking area outside of the building where the fMRI scanner is located in order to standardize the timing of cigarette exposure for all participants.
13. Undergo a 1-hour fMRI scan adhering to the procedures and Table 1 below:

Scanning Protocol/Data Acquisition: MRI is performed in a 1-hour session, which, in our experience, participants tolerate easily without discomfort or excessive motion. Prior to entering the scanning area, an approved MRI Technician or MRI User will review the participant's magnet safety form and will confirm that the participant has removed all metal and/or objects containing magnetic strips from their persons. Once the participant is approved to enter the scanning area, the participant will be placed supine in the scanner, wearing earplugs to muffle noise, and fitted with adjustable foam cushions to limit head motion. If a participant requires corrective lenses for vision, but does not have contact lenses, a set of plastic glasses that are approved for use in an MRI scanner will be provided to him/her. Participants will be provided with an emergency squeeze ball, so that they may interrupt the scan and/or be removed from the scanner if necessary. Head fixation will be assured through a foam-rubber device mounted on the headcoil.

CONFIDENTIAL

This material is the property of the University of Pennsylvania. Do not disclose or use except as authorized in writing by the study sponsor

Image acquisition is performed on a 3T Siemens Tim-Trio scanner with a FDA approved head coil. A T1-weighted multi-echo magnetization-prepared, rapid acquisition gradient echo (MPRAGE) structural image is acquired using standard parameters at 1mm resolution. This MPRAGE is used for functional image co-registration and transformation into standard template space. Resting BOLD fMRI will be obtained followed by the three task paradigms.

Task stimuli will be rear projected to the center of the visual field using a PowerLite® 7300 Video projector system (Epson American, Inc., Long Beach, CA) and viewed through a mirror mounted on the head coil. Participants will use a fiber optic response pad (FORP™ Current Design, Inc., Philadelphia, PA) made of non-ferromagnetic components. This MR-compatible button-box is used to record task responses and reaction times. Pulse and respiration are recorded as an index of physiological arousal during the task and to statistically reduce the effects of physiological noise in the fMRI data.

Resting State fMRI: Whole-brain functional MR images will be acquired while subjects rest with eyes closed over 39 axial, interleaving, 4-mm sections by means of a gradient-echo echo planar imaging sequence (150 volumes; echo time/repetition time, 27/2000 milliseconds; flip angle, 80°; field of view, 220 x 220 mm; image matrix, 64x64).

Task fMRI: BOLD images will be acquired using a whole-brain, single-shot gradient-echo (GE) echo-planar imaging (EPI) sequence with the following parameters: TR/TE=2000/30 ms, flip angle 90°, field of view (FOV)=192 mm, matrix = 96X96, isotropic voxel resolution 2.5 mm, slice thickness/gap=2.5/0mm, 38 slices axial-oblique parallel to AC-PC. In ongoing studies, we find these parameters produce robust signal in ventral brain regions, including ventral striatum and orbital/ventral prefrontal cortex, with little distortion or signal loss.

Food Cue Reactivity: The task will present (5 sec) 20 pictures of food rated (at Intake) as most appetizing and 20 pictures of food rated (at Intake) least appetizing, and 20 pictures of a water glass. Participants will be instructed to imagine tasting and eating the pictured food for as long as the food is presented. Order of presentation is randomized and the task consists of 60 events separated by an inter-stimuli interval (fixation point) ranging from 2-11 sec (mean 5.5 sec). As a secondary measure, food craving will be assessed prior to and after completion of the scan. The food craving assessment is the 3-item “desire” subscale of the reliable and valid state version of the Food Craving Questionnaire (FCQ-S). Total task time: ~10 minutes.

Food Reinforcement/Choice: Participants choose between a standard low effort monetary reward and either (on separate trials) a food or monetary reward of higher value and effort. Each trial presents a choice between a standard reward (27 button clicks for \$0.25) or exerting greater effort to earn a larger reward. In half of the trials, larger rewards will be \$0.50 (2 x standard value). In the remaining trials the larger reward will be double the calibrated snack portion (e.g., 20 M&Ms). Effort for more valuable rewards will vary from 27 to 775 responses in 25 log10 steps. Pairs of visual stimuli depicting the two options appear for 4.5 sec followed by a 3-14 sec inter-trial interval. Each pairing is presented twice, making 50 trials for each class. Left/right position of stimuli is randomized, as is trial type (monetary vs. food; effort levels). To increase motivation to choose food and monetary reward, participants are told they will complete the work and receive the outcome of 4 randomly selected food and monetary (maximum \$2.00) trials. Total task time: ~15 minutes.

Working Memory: We will use a 12-minute visual N-back task validated for fMRI studies of smokers. A total of 20 fractals (target-foil ratio 1:3) are presented for each condition (i.e., 0-back, 2-back, 3-back), and each condition (60 sec block) is repeated 3 times in pseudo-

TABLE 1: fMRI Session	
~Duration (mins.)	Activity
5	Structural Scans (localizer, MPRAGE)
10	Resting State BOLD fMRI
15	Food Reinforcement/Choice ^a
12	Working Memory ^{a,b}
10	Food Cue Reactivity ^a
2	B0 Map ^{*if time permits*}
Total Time in Scanner: ~54 minutes	
^a fMRI tasks will be presented in a fixed order	
^b Stimuli (Form A/B) will be counterbalanced within subject	

CONFIDENTIAL

This material is the property of the University of Pennsylvania. Do not disclose or use except as authorized in writing by the study sponsor

random block design experiment. Each fractal is displayed for 500ms followed by 2500ms inter stimuli interval. Total task time: ~12 minutes.

14. When all scans are completed, participants will be removed from the MRI scanner and be asked to complete a brief ~5-minute “work” task (i.e. clicking on a target a certain amount of times) based on their selections during the in-scanner Food Reinforcement/Choice task on a laptop computer.
15. Participants will receive the appropriate reward(s) (food and/or monetary) per the post-scan work task, as well as receive compensation for time and their preferred travel compensation per the study compensation schedule. At the end of the session, participants will be escorted to the exit of the imaging facility where they will be free to leave.

5.2.8 End of Recruitment and Retention Pilot Debriefing Call (After Scan 2 or last visit completed). After the participant has completed their final visit (Scan 2 or their last completed session after withdrawal or ineligibility), study staff will reach out to all participants enrolled in the recruitment and retention pilot to provide additional details about their participation in the pilot.

